Therapy with (Li-ESWT) for erectile dysfunction has been proposed as a new alternative in the management of erectile dysfunction (12, 22-25). Its mechanisms of action can be multiple, but are summarized in the increase in vascular flow to the corpora cavernosa generated by a process of neovascularization (26) secondary to angiogenesis promoted by endothelial growth factors such as vascular endothelial growth factor (VEGF), endothelial cell growth factors and cell proliferation nuclear antigen (27), in addition to the increase in the concentration of vasodilator substances such as nitric oxide. The therapy with Li-ESWT has been presented as a therapeutic option, which does not replace the other alternatives, but which adds efficacy to traditional ED management (28).

Likewise, therapy with radial waves arises as a new option for the management of this disease, which has been conducted by different specialists given the benefit shown in the increase of blood flow and muscle recovery for different musculoskeletal conditions. However, currently there are no controlled studies that report on the efficacy and safety of this therapy for the treatment of erectile dysfunction (16, 17). For this reason, it is pertinent to carry out a clinical trial that allows obtaining valid results and thus making reliable clinical decisions.

Objectives

Primary

To evaluate the effectiveness of radial shock wave therapy in patients with moderate erectile dysfunction ² measured as the increase in the average IIFE-EF score at the end of the treatment.

Secondary

- 1. To evaluate the effectiveness of radial shock wave therapy at one month of follow-up, with respect to the change in the average IIFE-EF score.
- 2. To evaluate the efficacy of radial shock wave therapy with respect to the average score of the erection hardness scale (EHS), at the end of the treatment and at one month of follow-up, in the intervention and control groups.
- 3. To evaluate the effectiveness of radial shockwave therapy, regarding the change in the use of sildenafil at the end of treatment and at one month of follow-up, in the intervention and control groups.
- 4. To compare the incidence of adverse events in the intervention and control groups.

² For this study moderate erectile dysfunction is considered a score on the IIEF-EF scale from 11 to 21, which includes the mild to moderate and moderate categories.

Materials and methods

Type of study

Randomized, double-blind clinical trial.

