Interventions

Each patient will be assigned randomly to one of the following groups:

- Arm 1 (Radial wave therapy + oral treatment): 6 radial waves' sessions. A weekly session of radial waves will be applied with the following parameters: 6000 pulses at 1.5-2.6 bar (depending on patient tolerance), with a frequency of 17Hz, the frequency should increase to 22HZ the first 500 impulses to create mild anesthesia in the area; in all the sessions of radial waves, 4000 impulses will be distributed in the body of the penis in scanning technique and 2000 impulses in the perineal area, specifically in the ischiocavernosus and bilateral bulbo-sponge muscles. During the period of therapy application, patients will receive oral treatment with sildenafil 4 according to the patient's degree of affectation.
- Arm 2 (Placebo therapy + oral treatment): 6 sessions of placebo therapy. There will be a weekly session of placebo wave therapy, using the respective device to prevent the patient from receiving the radial wave. The same parameters of the "real" therapy will be used: 6000 pulses at 2.6 bar, with a frequency of 17 Hz; in all the sessions of radial waves, 4000 impulses will be distributed in the body of the penis in scanning technique and 2000 impulses in the perineal area. During the period of therapy application, patients will receive oral treatment with sildenafil 5 according to the patient's degree of affectation.

The radial waves will be administered with the Masterpuls MP50 device from Storz medical.

Primary Outcome

The primary outcome of this study is the difference in the average score of the IIEF-EF scale (Annex 3) in at least 5 points at the end of the treatment.

Secondary outcomes

- IIEF-EF score after one month of follow-up.
- Erection Hardness Score (EHS) at the end of treatment and one month follow-up: The EHS is a unique Likert scale and the version validated in Spanish (35) will be used, which has the following score, 0: The penis does not change in size or hardness; 1: The penis increases in size but does

⁴ This is the standard treatment.

⁵ This is the standard treatment

not become rigid; 2: The penis is rigid but not enough to penetrate; 3: The penis is rigid enough for penetration but not completely hard; and 4: The penis is completely hard or rigid (Annex 4).

- Change in the dose or use of sildenafil.
- Incidence of adverse events.

Safety

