It will be determined by the presence of adverse events. These will be evaluated at the end of each of the therapies and a month of follow-up. This variable will be dichotomous as the presence or absence of adverse events. Additionally the type of adverse event and the degree of severity will be recorded.

Randomization

The assignment of patients to the treatment arms will be done with the method of randomization by balanced blocks of unequal cells. The assignment of the treatment will be centralized, so once the patient agrees to participate in the study and signs the informed consent, an email should be sent to the research center ([contact]) who will only inform the therapist which is the group (intervention or control) that corresponds to the patient.

To conceal the assignment sealed opaque envelopes will be used, this envelope will be opened once the request is generated in each center, after the patient has voluntarily accepted to participate in the study and the informed consent process has been carried out with signature of the written document.

Neither the patient, the attending physician, nor the professional who applies the questionnaires will know the group to which the patient was assigned.

Techniques, procedures, data collection and processing

The subjects who attend consultation for erectile dysfunction at the Boston Medical Group clinics in Bogotá (Colombia) and Lima (Peru), will be treated as usual according to the institutional management protocols and screened to determine if they meet the eligibility criteria. If so, they will be invited to participate in the research project and the informed consent process will be carried out in which the objectives, risks, benefits, procedures and other relevant research data will be explained.

Once the patient has voluntarily accepted to participate in the study and the informed consent document has been signed, an email will be generated to the research center to request the group to which the patient will be assigned.

A baseline measurement of the IIEF-EF and the EHS will be made before starting the intervention; In addition, the AMS questionnaire should be completed to rule out hypogonadism. Once the treatment is completed, patients must complete the IIEF-EF and EHS scales in the last treatment session. In this same session, the patient will be evaluated for adverse events; later, they will have

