a medical follow-up one month after the end of the treatment, in which measurements of effectiveness and safety of the therapy will be made again. If the patient cannot attend the medical follow-up, the surveys will be sent by email on the day of the follow-up appointment and the patient will be contacted by telephone (Figure 2).

Radial wave therapy will be applied with the following parameters: There will be a weekly session of 6 sessions of radial waves. A weekly session of radial waves will be applied with the following parameters: 6000 pulses at 1.5-2.6 bar (depending on patient tolerance), with a frequency of 17Hz, the frequency should increase to 22HZ the first 500 impulses to create mild anesthesia in the area; in all the sessions of radial waves, 4000 impulses will be distributed in the body of the penis in scanning technique and 2000 impulses in the perineal area. The application at the perineal level should be performed with the patient in the supine position in a low lithotomy position, the testicles should be slightly raised to apply the wave on the perineal musculature (ischiocavernosus and bilateral bulbospongiosus).

The placebo therapy will be done with the same machine and the same parameters as the actual therapy, but the adjustment will be made in the handpiece to eliminate the effect of the radial waves.

If there is a difference between placebo therapy and radial wave therapy, patients in the placebo arm will receive the intervention arm scheme, one month after the initial treatment.

All clinical data will be recorded in the electronic medical record of Boston Medical Group and in the database of the study, in the latter a code will be used for the identification of research subjects, thus avoiding the use of the personal patient data. At the end of the collection of the total sample, the missing clinical information will be extracted from the electronic medical record. This information will be exported to a flat file for the corresponding statistical analysis.

The research team will hold meetings every two weeks to monitor the study to validate the data of the base.

Follow-up

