The research subjects will be followed up one month after the end of the treatment. In the event that the patient cannot attend the follow-up, the respective scales will be sent to his e-mail so he can process them and return them by the same means; if after 3 days no response is received, a research assistant will call him and apply the questionnaires by telephone.

Statistical Analysis

A descriptive analysis of the individuals' baseline characteristics linked to each treatment arm will be made, estimating measures of central tendency and dispersion in the case of continuous variables, and measures of relative and absolute frequency for categorical variables.

To evaluate the effectiveness of the therapy, the change in the IIEF-EF scale will be compared at the end of the treatment with the baseline score for each of the arms, using parametric tests in case the

data present a normal distribution, or nonparametric tests otherwise. This same analysis will be done for the scores at the one-month follow-up.

For the EHS scale, the change in at least 1 point will be evaluated, in any of the established measurements. The association between the change in the score and the received treatment will be evaluated estimating the relative risk with its respective confidence interval.

The percentage of patients that decrease or discontinue the use of sildenafil in each group will be estimated, comparing the proportion between the groups at the end of the therapy scheme and the month of follow-up, using the Chi-square test.

The incidence of adverse events for each of the intervention groups will be estimated and the value between them will be compared using the Chi-square test.

In addition to the comparison between groups, stratified analyzes will be performed with multivariate regression models to determine how each intervention adjusted for covariates, such as comorbidities or additional treatments.

An interim analysis will be done once 60% of the total number of patients has completed the treatment (main outcome).

Expected impact

The main contribution of this study is for the scientific community and for patients with erectile dysfunction, by collecting scientific evidence of quality that allows to make a decision about the use of radial waves for the management of erectile dysfunction.

Ethical aspects

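### Secondary objective 2 names the average EHS at two visits, but the only EHS-specific analysis planned is a responder relative risk, and its visit rule can be read two ways

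*Combined protocol and SAP*

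**What the plan says.** All references are to the combined protocol and SAP.

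- **Objectives, Secondary, item 2:** for both arms, efficacy is to be evaluated "with respect to the average score of the erection hardness scale (EHS), at the end of the treatment and at one month of follow-up".
- **Secondary outcomes:** "Erection Hardness Score (EHS) at the end of treatment and one month follow-up". The scale runs from 0 to 4.
- **Techniques, procedures, data collection and processing:** EHS is measured at baseline. After that, "patients must complete the IIEF-EF and EHS scales in the last treatment session", and at the one-month medical follow-up "measurements of effectiveness and safety of the therapy will be made again".
- **Statistical Analysis:** "For the EHS scale, the change in at least 1 point will be evaluated, in any of the established measurements". The association with treatment is then "evaluated estimating the relative risk with its respective confidence interval".

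The same section handles the other repeated outcomes differently. For IIEF-EF it describes the end-of-treatment comparison and adds: "This same analysis will be done for the scores at the one-month follow-up". For sildenafil use it specifies "comparing the proportion between the groups at the end of the therapy scheme and the month of follow-up".

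**The concern.** The objective is stated as an average score per arm at two times. The analysis is a yes/no response, compared by a ratio of proportions. A plan followed to the letter would produce no comparison of average EHS, so objective 2 could not be answered in its own terms. A mean comparison added later would not be prespecified.

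The second issue is smaller. A change in 'any' of the measurements could mean a response judged at each visit, giving two relative risks, or a response at either visit, giving one. The one-month visit is the only planned assessment after treatment ends. A figure that merges the two visits could therefore conceal whether an EHS effect lasts.

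**Working it through.** **No plan figure to reproduce.** The documents give no EHS effect, standard deviation or responder rate. The check is a comparison of texts, followed by arithmetic on stated examples.

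**Step 1. Does anything else in the Statistical Analysis section supply the mean EHS?**

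- The descriptive paragraph covers baseline characteristics only.
- The parametric or nonparametric comparison is specified for IIEF-EF, and the sentence extending it to one month refers back to that scale.
- The sentence on multivariate regression names no outcome, scale or visit.

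The relative risk is therefore the only EHS-specific analysis.

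**Step 2. Can one measure stand in for the other?** The 33 patients per arm come from the Sample size section (before the allowance for losses). The gains are chosen to make the point.

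- *Equal responders, unequal means.* In each arm 17 of 33 gain and 16 are unchanged; the gain is 2 points in one arm and 1 point in the other. Relative risk = (17/33)/(17/33) = 1.00. Difference in mean change = 34/33 − 17/33 = 17/33 = 0.52 points.
- *Equal means, unequal responders.* In one arm half gain 2 points and half gain none: mean change 0.5 × 2 + 0.5 × 0 = 1.0, responders 50%. In the other arm everyone gains 1 point: mean change 1.0, responders 100%. Relative risk = 100/50 = 2.0 with no difference in mean change.

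Each measure can miss what the other shows.

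**Step 3. Does the reading of 'any' matter?** For a per-visit response rate p, the either-visit rate lies between p (the same patients respond twice) and the smaller of 1 and 2p (no overlap). At p = 40% that is 40% to 80%.

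The size was illustrated by simulation. All inputs are assumptions, except that EHS 4 is excluded at baseline (exclusion criterion 1):

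- a latent normal score at baseline, end of treatment and one month, cut into EHS categories, 1,000,000 draws per setting;
- baseline EHS 0/1/2/3 in 5/15/45/35% of patients;
- latent improvement of 0.4 in both arms;
- correlation 0.5 between baseline and follow-up, and 0.7 between the two follow-up visits;
- treatment effect of 0.7 latent units at end of treatment.

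Response is a gain of at least 1 point from baseline.

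| Pattern | End of treatment | One month | Either visit |
|---|---|---|---|
| Effect gone by one month | 0.748/0.487 = 1.54 | 0.487/0.487 = 1.00 | 0.779/0.612 = 1.27 |
| Effect sustained | 1.54 | 1.54 | 0.850/0.612 = 1.39 |

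**Sensitivity.** The baseline correlation was varied over 0.3, 0.5 and 0.7, the between-visit correlation over 0.5, 0.7 and 0.9, and three baseline mixes were used. The either-visit relative risk for the vanished effect was then 1.20 to 1.47; for the sustained effect it was 1.30 to 1.59. The two ranges overlap, so a single either-visit figure may not tell the patterns apart. Raising only the common improvement from 0.4 to 0.8 in the central case gives 1.16 for the vanished effect. Across everything tried the span is about 1.16 to 1.47. The treatment effect of 0.7 was not varied, so this span is not a bound.

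**The case against.** The strongest defence has three parts.

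1. *The planned analysis is legitimate.* The Secondary outcomes section lists the EHS at two times without saying average. A one-point responder definition is reasonable for a five-category scale, and the relative risk compares the arms with a confidence interval. This stands. A reader might infer that the trial has no EHS efficacy comparison, or that the relative risk is inferior to the mean. The documents support neither, and the second example in Step 2 shows the mean missing a difference that the relative risk detects. What remains is that the objective and the analysis name different measures.

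2. *The visits are fixed elsewhere.* Objective 2 and the Secondary outcomes section both name two times, and the IIEF-EF and sildenafil analyses treat each visit separately. This largely stands: one relative risk per visit is the more natural reading. A reader might infer that the plan does pool the visits; it does not say so. The sentence merely permits it, and the masking in Step 3 arises only under that less natural reading.

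3. *The numbers are invented inputs.* This is true of the simulation, which shows direction and rough size only. For the same reason no statement about EHS power is made here. The textual mismatch and the arithmetic in Step 2 do not depend on those inputs.

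A reader might also infer that a one-point worsening counts as a response, because no direction is given. The aim is evidently improvement, so this is only a wording gap.

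**Conclusion.** The point holds. As written, no planned analysis estimates the average EHS by group that secondary objective 2 names, and the responder relative risk is not a substitute. In the worked example a relative risk of 1.00 sits beside a mean difference of 0.52 points, and the opposite pattern is equally possible. This conclusion rests on the text and simple arithmetic.

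The wording of 'any' is a secondary ambiguity. If it were taken as either visit, an effect with relative risk 1.54 at end of treatment and 1.00 at one month would be reported as 1.27, or about 1.16 to 1.47 across the assumptions tried, all of them outside the documents.

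It would go too far to read this as a threat to the trial's main result: EHS is a secondary outcome and the primary IIEF-EF conclusion is unaffected. The plan should be corrected, but the flaw is not fatal.

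**What to change.** In the Statistical Analysis section, add: *At end of treatment and, separately, at one month, mean EHS (SD) is reported for each arm, and the arms are compared by the baseline-adjusted difference in mean EHS with its 95% confidence interval.* Keep the relative risk, defined as an increase of at least 1 point from baseline and reported once for each of the two visits. This also settles the direction of change.

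If the sponsor prefers the responder measure, rewording objective 2 as the proportion gaining at least 1 point at each visit removes the mismatch equally well. The two visits should still replace the word 'any'.

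The cost is wording and a small amount of analysis. No new data are needed: EHS is already due at baseline, at the last session and at one month.

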Radial waves are generated by collision of solid bodies. The compressed air accelerates a projectile (bullet) that hits an impact body and part of the produced kinetic energy is transmitted to this body generating a translational movement in a short distance at a low speed until the coupled tissue or the hand piece decelerates its movement (15, 20).

The movement of the impact body is transferred to the patient's tissue at the point of contact, from where it propagates in the form of a radial pressure wave, which in the skin or superficial tissue is strong and decreases as it advances to deeper tissues (15, 20).

The effect of radial waves is less intense than focal shock waves, causes the disintegration of fibrosis and calcifications, and increases blood microcirculation and metabolic activity in the treated site (15, 20). There is evidence that radial wave therapy has a poor penetration to tissue (3cm), a low impact and limited biological effects (20, 21), however, this therapy has demonstrated effectiveness in the management of pain, muscle and tendon inflammation (15).

Although the effect of this type of waves is not known in erectile dysfunction, the effect on microcirculation increase suggests that it may be useful as a complementary therapy to the treatments currently used. In addition to this there is low-quality evidence that suggests a possible beneficial effect of radial waves.

Justification

Erectile dysfunction is a pathology with a moderate prevalence which increases and worsens as the population ages. It affects not only the sexual and reproductive health of the sufferer and his partner, but also his mental health, often producing disorders depressives that diminish the quality of life of people and their families.

Pharmacological treatment is not effective in 100% of patients and does not lead to changes in the physiology-pathology of erectile dysfunction (14), but acts as an adjuvant in the symptomatology, therefore, the management of erectile dysfunction should focus on the treatment of the pathophysiological causes that generate it and therefore other treatment options that can act in this way should be sought.

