Research hypothesis

Ho: The change in the score of the IIEF-EF scale in patients with moderate erectile dysfunction³, treated with radial wave therapy, is equal to those who receive placebo therapy.

Ha: The change in the score of the IIEF-EF scale increases at least five points in patients with moderate erectile dysfunction treated with radial wave therapy, compared with the score of patients receiving placebo therapy.

Study population

Patients diagnosed with erectile dysfunction of vascular origin who are treated at the Boston Medical Group facilities in Bogotá.

Inclusion criteria

- 1. Men older than 18 years
- 2. Erectile dysfunction presents for more than 3 months in more than 50% of intercourse.
- 3. IIEF-EF score between 11 and 21.
- 4. Patient who agrees to enter the study through the signing of an informed consent.

Exclusion criteria

- 1. EHS score of 4
- 2. Bladder, prostate or colon cancer.
- 3. Patients with ED of psychological origin.
- 4. Patients with spinal cord injury.
- 5. Patients with anticoagulant use.
- 6. Patients with sickle cell anemia.
- 7. Patients with clinical suspicion of hypogonadism (AMS greater than 36, Annex 1).
- 8. Patients with infections or active lesions of the penis or pubic area.
- 9. Patients with ED secondary to drug treatment (antiandrogenic therapy, antidepressants, use of corticosteroids, antiparkinsonians, antipsychotics).
- 10. Radical prostatectomy or other radical pelvic surgery.
- 11. Antecedents of pelvic radiotherapy.
- 12. Patients with penile implant.
- 13. Endocrine diseases that occur with ED: acromegaly, gigantism, Addison's disease, hyperprolactinemia, androgenic deficiency.
- 14. Patients with neurological diseases (Parkinson's, CVD, dementia of any origin)

³ For this study moderate erectile dysfunction is considered a score on the IIEF-EF scale from 11 to 21, which includes the mild to moderate and moderate categories.

Sample size

Assuming that the placebo plus drug group has an average change in the score of the IFE-EF scale of 5 points and that the new wave therapy must have an additional change of at least 5 points to be considered clinically relevant, for a power of 80% and a one-tailed level of significance of 97.5%, with a standard deviation of 8 points, a sample size of 33 patients was estimated for each group. Adjusting for a percentage of losses of 20%, the size per group is 40 patients, for a total of 80 patients in the study. These calculations were performed in Stata 15.1®.

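### The sildenafil outcome counts every decrease or stop as effectiveness without regard to erectile function, so a stop because the drug failed scores the same as a reduced need

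*Combined protocol and SAP*

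**What the plan says.** The outcome appears in three places in the combined protocol and SAP.

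- Item 3 of the list under Objectives, Secondary, reads: "To evaluate the effectiveness of radial shockwave therapy, regarding the change in the use of sildenafil". Both the last session and the one-month visit are named as time points.
- Secondary outcomes: "Change in the dose or use of sildenafil". There is no further definition.
- Statistical Analysis: "The percentage of patients that decrease or discontinue the use of sildenafil in each group will be estimated", with the arms compared by chi-square at both time points.

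Four other places bear on it.

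- Interventions: both arms receive sildenafil during the therapy period, dosed by severity. There is no rule for lowering or stopping it, and nothing is said about its use after the last session.
- Justification: "Pharmacological treatment is not effective in 100% of patients".
- Randomization: "Neither the patient, the attending physician, nor the professional who applies the questionnaires will know the group".
- Techniques, procedures, data collection and processing: "A baseline measurement of the IIEF-EF and the EHS will be made before starting the intervention". IIEF-EF and EHS are repeated at the last session and at one month. The Abstract lists medication use among the measurements at the same time points.

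**The concern.** An effectiveness outcome should move in one direction when patients do better. This one does not. Sildenafil use can fall because a man needs less of it, but also because it did not work, because he could not tolerate it, or, at one month, because the planned course had ended. The protocol itself accepts that drug treatment fails in some men, so the second route is foreseeable. All these routes add to the same percentage, and objective 3 reads a higher percentage as better.

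At stake is what this comparison can show. If other-reason stops are equal in the two arms, they shrink the difference. If waves work, failure stops should be more frequent under placebo, which shrinks it further. Only an excess of such stops in the wave arm would create an apparent benefit. The primary outcome and the separate IIEF-EF and EHS comparisons are not touched.

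**Working it through.** **What the text settles.** Objective 3 makes the outcome a measure of effectiveness. The analysis counts any decrease or stop. No section records the reason for a change or sets a condition on function. The planned regression adjusts for comorbidities and additional treatments, which does not classify stops. IIEF-EF and EHS are compared by arm, which cannot show whether the men who stopped are the men who improved.

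**What the text does not settle.** The documents give no rate for this outcome, so there is no figure of the plan's own to reproduce. The rates below are assumptions and show only direction and range.

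**Inputs.** n = 33 evaluable per arm, taken as stated under Sample size; two-sided 0.05. Assumed: p = share who truly need less sildenafil; f = share of the remaining men who decrease or stop for another reason.

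**Formulas.** Counted rate r = p + (1 − p)·f. For the pooled two-proportion test, with r̄ the mean of the two rates:

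- SE0 = √[2·r̄(1 − r̄)/n]
- SE1 = √[r1(1 − r1)/n + r2(1 − r2)/n]
- power ≈ Φ[(r1 − r2 − 1.96·SE0)/SE1]

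With p = 50% vs 20% and no other stops: r̄ = 0.35, SE0 = 0.1174, SE1 = 0.1115, and (0.30 − 0.2301)/0.1115 = 0.627, so power is 0.735.

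**A true benefit (p = 50% waves, 20% placebo)**

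| f, waves / placebo | Counted rates | Power |
|---|---|---|
| 0 / 0 | 50% vs 20% | 73% |
| 10% / 10% | 55% vs 28% | 61% |
| 30% / 30% | 65% vs 44% | 40% |
| 10% / 20% | 55% vs 36% | 34% |
| 10% / 30% | 55% vs 44% | 14% |

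For example, in the last row the placebo rate is 0.20 + 0.80 × 0.30 = 0.44.

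Other assumed rates show the same pattern. With 40 per arm and a true reduced need of 30% vs 10%, power is about 61%. Adding failure stops in 5% vs 20% of all men makes the counted rates 35% vs 30%, and power falls to about 7%.

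**No true benefit (p = 20% in both arms), chance of a significant result favouring waves (nominal 2.5%)**

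| f, waves / placebo | Counted rates | Chance |
|---|---|---|
| 10% / 5% | 28% vs 24% | 6% |
| 20% / 10% | 36% vs 28% | 10% |
| 30% / 10% | 44% vs 28% | 27% |

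**What a joint count would do.** Let s be the share of true reducers who meet a function condition at the same visit, and g the share of other-reason stoppers who meet it. The joint rate is p·s + (1 − p)·f·g.

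- With g = 0, s = 80% gives 40% vs 16% and power of 59%; s = 60% gives 30% vs 12% and 43%.
- At equal other stops of 10%, the joint count has more power than the raw count only if s is at least 83% (g = 0) or 88% (g = 25%).
- At equal other stops of 30%, those thresholds are 56% and 72%.
- In the 27% false-benefit case, with s = 100% and g = 25%, the joint rates are 0.20 + 0.80 × 0.30 × 0.25 = 26% and 0.20 + 0.80 × 0.10 × 0.25 = 22%. The chance falls to about 6%, not to 2.5%.

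**The case against.** The strongest reply is that the mechanism is inferred. That the drug fails in some men does not mean those men stop it within a six-week blinded course. Under severity-based dosing, a poor response could as well raise the dose, which is not counted at all. That stands: no section shows that failure stops are common.

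A second reply is that the plan only estimates and compares a percentage and never calls a stop a success. IIEF-EF and EHS are compared at the same visits, so a fall in use without better function would show at arm level, and recorded adverse events help to identify intolerance. This lowers the risk of misreading but does not remove it. Objective 3 makes the percentage an effectiveness measure, and arm-level comparisons do not link the two facts within a man.

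A third reply concerns the obvious remedy. The plan has its own EHS threshold ("For the EHS scale, the change in at least 1 point will be evaluated"), and it is tempting to count only men who lower their use and gain a point. That would be too strict. A man at EHS 3, already rigid enough for penetration, who stops sildenafil and stays at 3 would fail. So would a man whose baseline was measured on the drug and who keeps his function without it. When baseline was taken is itself unclear. The sample-size assumption ("Assuming that the placebo plus drug group has an average change in the score of the IFE-EF scale of 5 points") suggests that baseline precedes sildenafil, but attendees are managed under the clinics' usual protocols, so some may already be taking it. This reply stands, and the remedy below avoids that requirement.

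**Conclusion.** The point holds as one of definition. Followed as written, the rule gives a stop for drug failure or intolerance the same weight as a reduced need, and nothing else in the plan separates them at patient level.

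The likely consequence is a diluted or hidden benefit. A reader might infer that the outcome is set up to produce a false benefit. The documents do not support that: it would need more other-reason stops with waves than with placebo, while both arms have the same sildenafil rule and patient, attending physician and questionnaire staff are blinded. It remains possible but is less likely. A reader might also take the 14% or 27% above as estimates. They are not; both need other-reason stops of 30% in one arm against 10% in the other, and every rate is assumed.

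The effect is confined to one secondary outcome. The change is worth making because it is cheap, but the trial's main conclusion does not depend on it.

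**What to change.** Keep the raw percentage of decreases and stops, and its chi-square test. Add, at the end of treatment and at one month, the percentage who decreased or stopped sildenafil **and** had adequate function at the same visit. One workable definition is EHS of at least 3 and not below baseline, with IIEF-EF above baseline (or not below baseline if baseline was measured on sildenafil). State which baseline applies. Base any claim of reduced need on this joint percentage. Report the remaining decreases and stops separately, with the reason where the medical record gives it.

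Cost: no new visit or scale, since EHS, IIEF-EF and medication use are already collected at these time points. The joint event rate is lower, so power is probably lower when other-reason stops are few; there the gain is in meaning. The joint count also remains imperfect: a man who cuts his dose for side effects but functions well on what is left still counts, which is why the reasons should be shown beside it.
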